9.7. Telephone interviews

At approximately ten weeks post-baseline, telephone interviews will be conducted by the trial qualitative researcher with up to 20 participants (10 from each treatment group) in order to collect information on patients' experience of their treatment, including psychological and social impact. Telephone interviews will last up to 60 minutes and will be recorded digitally. Further details and description of proposed analysis is given in section 12.3 (Qualitative component).

9.8. Radiographic Evaluation

Pre-operative, intra-operative and post-operative X-rays will be taken for each participant as per routine care. In some cases, particularly where recovery is complicated, further X-rays within the 12-week trial period may also be taken. At the end of the study, pre-, intra- and post-operative X-rays, plus any further X-rays taken within the trial period will be reviewed by the CI in a blinded fashion on a participant-by-participant basis. For each participant, the CI will record the following on a bespoke data collection form:

- Fracture classification (Weber A, B or C)
- Fracture pattern (medial malleolar fracture or deltoid ligament injury)
- Integrity of surgical metalwork (displaced or undisplaced)
- Evidence of post-operative fracture healing (yes/no)

The data collection forms will be returned to the CTU for entry into the trial database. Research teams at local sites will liaise with their X-ray departments to arrange anonymisation and transfer of images. Instructions of procedures by which X-rays are collected, labelled, stored and sent are detailed in a separate work instruction.

10. INTERVENTION DETAILS

10.1. Removable support boot

Patients in the boot group will be fitted with a removable support boot/pneumatic walker brace. To ensure the trial is pragmatic, any model of boot may be used, providing it meets the following specifications:

- Has at least two air cells to provide compression
- Rigid (e.g. plastic) anterior and posterior outer sections. NB: Boots with soft (e.g. foam only) anterior sections are not suitable as they offer reduced support to the ankle
- Suitable for weight-bearing and removable to allow for mobilisation of the ankle

The CI and Lead Site Research Physiotherapist will assess the specifications of support boots prior to their use in the trial to ensure their suitability to deliver the trial intervention.

Patients in the boot group will be given a trial specific advice leaflet advising regular exercise by a physiotherapist trained in the requirements of the protocol e.g. regular removal for exercise during the day/boot off at night as tolerated. The leaflet will provide illustrated instructions for completion of the following exercises; Straight leg raise, Ankle dorsiflexion/plantarflexion, Ankle inversion/eversion, Calf stretch, and Resisted plantarflexion. Patients will be encouraged to mobilise their ankle as often in a day as pain allows (recommended at least 3 times a day.)

Participants will be advised on gait re-education with crutches and will progress to weight-bearing as able.

10.2. Plaster Cast

The plaster cast used will be a standard below knee rigid plaster cast shell with soft lining to provide support in a fixed position to the ankle. The plaster cast is rigid enough to support weight-bearing and is custom built for the patient.

The plaster group will also receive a trial specific advice leaflet on plaster care/mobilisation of free joints. The leaflet will provide illustrated instructions of the following exercises: Toe flexion/extension, Static quads and Straight leg raises. Patients will be encouraged to mobilise their ankle as often in a day as pain allows (recommended at least 3 times a day.)

Participants will be advised on gait re-education with crutches and will progress to weight-bearing as able.

10.3. Associated Risks

The risks associated with participating in the ART study are no different to the risks of receiving standard treatment outside the study.

However, known complications include: blisters, pressure sores, failure of fixation, operation/revision surgery, wound infections, compartment syndrome, deep vein thrombosis (DVT), nerve injury, wound breakdown, and pulmonary embolism.

Participants randomised to plaster may experience more pressure sores, stiffness, difficulty accessing and monitoring wounds and similarly, participants in a support boot may experience problematic wounds.

11. ASSESSMENT OF SAFETY

11.1. Standard definitions

Adverse events (AE) are defined as any untoward medical occurrence in a clinical trial subject and which do not necessarily have a causal relationship with the treatment.

Adverse reactions (AR) are defined as an event that is considered to have a suspected causal relationship to the trial intervention (plaster or support boot.)

Serious adverse events (SAE) are defined as any untoward and unexpected medical occurrence that:

- Results in death
- Is life-threatening¹
- Requires hospitalisation or prolongation of existing inpatients' hospitalisation,
- Results in persistent or significant disability or incapacity
- Is a congenital anomaly or birth defect

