11.2. Reportable events

In the ART trial, all SAEs (as defined above) will be reported to PenCTU regardless of causality. Events which are not serious will not be collected or reported as adverse events but complications listed in section 10.3 will be reported as outcome measures.

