11.3.2. Assessment of expectedness

SAEs deemed to be possibly, probably or definitely related to trial participation will be classified as SARs. In such cases, the PI or authorised delegate will make a judgement on whether the event is expected or unexpected. The assessment of expectedness will be made with reference to the known risks listed in section 10.3. An event will be classed as unexpected if it is not listed in protocol section 10.3.

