13.5. Trial Steering Committee

The Trial Steering Committee (TSC) is responsible for the overall supervision of the trial, including overseeing recruitment, ensuring milestones are achieved and general scientific probity is maintained. In the absence of the DMC, the TSC will take on the role of reviewing adverse events, maintaining safety and will make recommendations for the premature discontinuation of the study where necessary.

The TSC will be chaired independently and will comprise of 6 full members; 3 independent experts (clinician(s)/statistician(s)), the Chief Investigator, and a service user representative. The Trial managers, data manager, sponsor and a funder representative will be invited to TSC meetings as observers. Members will meet at least annually as part of the Trial Steering Committee and will follow functions according to the Medical Research Council Good Clinical Practice guidelines³³. The composition and function will be described in a TSC charter prepared prior to study commencement.

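### Section 11.1 makes unexpectedness part of the SAE definition, so read literally a serious complication listed in 10.3 falls outside SAE reporting, in contradiction to 11.3, 11.3.2 and 11.4.1

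*Protocol*

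**What the plan says.** Section 11.1 defines adverse events without any reference to expectedness: "Adverse events (AE) are defined as any untoward medical occurrence in a clinical trial subject". The SAE definition that follows adds a condition: "Serious adverse events (SAE) are defined as any untoward and unexpected medical occurrence that", and then gives the seriousness criteria (death, threat to life, hospitalisation and so on).

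Section 11.2 makes that definition operative: "In the ART trial, all SAEs (as defined above) will be reported to PenCTU regardless of causality". It adds that non-serious events are not collected as adverse events, but that "complications listed in section 10.3 will be reported as outcome measures".

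Section 10.3 lists ten known complications: blisters, pressure sores, and "failure of fixation, operation/revision surgery, wound infections, compartment syndrome, deep vein thrombosis (DVT), nerve injury, wound breakdown, and pulmonary embolism".

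Section 11.3.2 takes SAEs already judged at least possibly related and asks whether each is expected, by reference to 10.3: "An event will be classed as unexpected if it is not listed in protocol section 10.3". Section 11.4.1 sends SAEs periodically to the sponsor, the chief investigator and the Trial Steering Committee (TSC), and reserves expedited ethics committee reporting for related SAEs that are unexpected.

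Section 13.4 states that there is no data monitoring committee. Section 13.5 assigns its safety role: "In the absence of the DMC, the TSC will take on the role of reviewing adverse events".

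**The concern.** Expectedness normally decides how fast a serious event is passed on, not whether it counts as serious. Section 11.1 uses it as an entry condition. The serious events that the protocol itself foresees after ankle fixation are then the ones that its definition leaves out.

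Two things are at stake. The first is oversight. The TSC takes the place of a data monitoring committee and may recommend stopping, and the only periodic safety report that the protocol promises it is the SAE report. The second is ascertainment. A site that applies 11.1 to the letter and a site that works from 11.3 onward could classify the same readmission differently. Section 4.2.2 names adverse events among the comparisons between treatments. Since non-serious events are not collected as adverse events, that comparison rests on SAEs.

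**Working it through.** No figure in the protocol bears on this point, so the check consists of reading the definitions together.

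1. From 11.1: an SAE is an event that is untoward, unexpected and meets a seriousness criterion.
2. From 11.3.2 with 10.3: unexpected means not listed in 10.3, so a listed event is expected. Section 11.1 does not define the word, and the protocol defines it nowhere else.
3. From 1 and 2: no event listed in 10.3 can be an SAE, however serious it is.
4. From 11.2: only SAEs under the 11.1 definition are reported to the trials unit. By step 3, a serious listed event is not among them.
5. The SAE form, 24-hour limit and register (11.3), the severity and causality assessment (11.3.1) and the periodic report (11.4.1) all attach to SAEs. A serious listed event reaches none of them.

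The table compares the text as written with the same text without the two words *and unexpected*.

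| Event | SAE as written | SAE without the two words | Expedited to ethics committee, as written / without the words |
|---|---|---|---|
| Serious, listed in 10.3, related | No | Yes, expected | No / No |
| Serious, listed in 10.3, unrelated | No | Yes | No / No |
| Serious, not listed, related | Yes | Yes, unexpected | Yes / Yes |
| Serious, not listed, unrelated | Yes | Yes | No / No |
| Not serious, listed in 10.3 | No | No | No / No |

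Only the first two rows change, and only in SAE status. The expedited column is the same on both readings.

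The contradiction with the later sections can be seen in three places:

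- **11.3** treats a hospital admission found in a resource use questionnaire as a possible SAE, with no condition on expectedness.
- **11.3.2** asks for a choice between expected and unexpected. Under 11.1 every event that reaches this step is already unexpected, so the choice has one possible answer. The order is also circular: 11.1 needs expectedness settled before an event becomes an SAE, while 11.3.2 assigns that judgement only to SAEs already found to be related.
- **11.4.1** restricts expedited reporting to unexpected related SAEs. That restriction does nothing if all SAEs are unexpected.

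**The case against.** The strongest reply is that this is one stray phrase. The rule about 10.3 sits in 11.3.2 and is stated there for related SAEs; carrying it back to 11.1 is an inference. The contrast in 11.2 turns on seriousness, and 11.3 has no expectedness filter, so a site following 11.2 to 11.4 would probably report a readmission for thrombosis. A separate Work Instruction, not shown, may make this clear. This stands in part: how sites will behave cannot be judged from the protocol. But 11.2 points back expressly to the definition in 11.1, and section 11.3 gives the Work Instruction the procedures, not the definition.

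A second reply is that 11.2 deliberately carves listed complications out of SAE reporting. The sentence does not say so for serious ones, and under a carve-out the reference to 10.3 in 11.3.2 would have no purpose. The sections would still need reconciling.

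Four stronger readings are tempting and are not supported:

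- A reader might infer that these events are lost to the trial. They are not: 7.2.4 records them to 12 weeks after surgery, with severity or site for several, and 12.2.3 compares them between arms by adjusted regression.
- A reader might infer that expedited ethics reporting suffers. The table shows that it does not.
- A reader might size the problem by applying the 6.6% wound infection rate quoted in section 3 to the boot arm. The protocol does not limit that rate to infections meeting a seriousness criterion, and it gives no admission rate.
- A reader might infer that the excluded events are those most likely to differ between boot and plaster. Section 3 calls the evidence on complications conflicting and inconclusive, and 10.3 does not suggest a difference in fixation failure.

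**Conclusion.** The contradiction is real, and the definition is wrong as written. Taken literally, all ten complication types in 10.3 are outside SAE reporting even when they are life-threatening or lead to admission, and the expectedness step can return only one answer. The loss is confined to prompt reporting, severity and causality assessment, the SAE register, the periodic report to the TSC, and uniform SAE ascertainment across sites. The primary outcome, the sample size and the planned comparison of complications are untouched. The number of events affected cannot be derived from the protocol.

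The conclusion assumes that *unexpected* in 11.1 has the meaning given in 11.3.2, the only one available. If sites apply the usual sense of an SAE instead, the practical effect shrinks, but 11.1 still conflicts with the sections that follow it. In a trial without a data monitoring committee, it should be corrected.

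**What to change.** Delete *and unexpected* from the SAE definition in 11.1, so that an SAE is any untoward medical occurrence meeting one of the listed seriousness criteria. Keep expectedness in 11.3.2 and 11.4.1 only, where it decides expedited reporting. Add one sentence to 11.2 stating that a 10.3 complication meeting a seriousness criterion is reported as an SAE as well as an outcome. Sections 11.1, 11.2, 11.3.2 and 11.4.1 then agree, and the Work Instruction should be checked against them.

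If the sponsor did intend a carve-out, it would have to be written out explicitly, with scheduled reports of serious complications to the TSC and a revised 11.3.2. That is a longer amendment for less prompt information.

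The cost of the preferred change is one deleted phrase, one added sentence and a few more SAE forms.

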11.2. Reportable events

In the ART trial, all SAEs (as defined above) will be reported to PenCTU regardless of causality. Events which are not serious will not be collected or reported as adverse events but complications listed in section 10.3 will be reported as outcome measures.

11.3. Procedures for Serious Adverse Event reporting

Procedures for collecting and reporting SAEs will be described in a separate trial-specific Work Instruction and will be discussed during investigator site initiation meetings.

SAEs may be identified via patient report at clinic visits or from receipt of resource use questionnaires which indicate a hospital admission. All SAEs will be reported to CTU using a bespoke Serious Adverse Event reporting form (SAE form). PIs or delegated staff must fax/email the completed SAE form to CTU within 24 hours of becoming aware of the event. The SAE report form will include a description of the event and an assessment of severity and causality as described below. PenCTU will maintain a register of all reported SAEs.

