4.2.2. Secondary objectives

[figure not shown]
- To determine whether there is a difference in quality of life between the two treatments.
- To determine whether there is a difference in healing, complications and adverse events between the two treatments.
- To determine whether there is a difference between return to work, driving and usual activities between the two treatments
- To determine which is the most cost-effective treatment option if provided in the NHS.
- To explore patient experiences and the psychological and social impact of their treatment.

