7.5. Adverse events

Serious adverse events will be collected from the point of randomisation at each data collection time point for the duration of the study. See section 11 (Assessment of safety) for details.

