9.4.2. End of 4-week follow up visit procedures

A member of the research team will ensure the following before the patient leaves the hospital:

- A copy of the 5-week follow-up questionnaires (and a freepost envelope) will be given to participants. They will be instructed on how to complete the questionnaire using their preferred option (online, phone or post). The importance of completing the questionnaire within 3-10 days will be emphasised. Participants will be encouraged to complete the questionnaire online. If they would prefer not to use the online method, they will be encouraged to complete over the phone. Those participants, who state that they are unable to complete the questionnaire online or by telephone, will use postal completion. Participants who are completing questionnaires online will be emailed to access this approximately 3 days after their 4 week clinic appointment. Participants who have opted for telephone completion will be telephoned approximately 5 days after their 4 week clinic appointment. Participants will be encouraged to have the paper version of the questionnaire by their side during the phone call.
- The patient has their Patient Diary and is aware that they will be receiving questionnaires in approximately 6 weeks' time by post/email and that they may be contacted in the event that the questionnaires are not returned so as to prompt for return or to complete the questionnaire over the telephone.

The research team will also ensure that the patient's continuing participation in the trial is appropriately recorded in the hospital records in accordance with local practice.

Completed questionnaires and CRF pages will be sent to PenCTU using FREEPOST envelopes.

9.5. 5-week follow-up questionnaire completion

The 5-week follow-up requires participants to complete a questionnaire comprising the following:

- Olerud and Molander (1984) ankle score (see section 7.1)
- EQ-5D-5L (see section 7.2)

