PenCTU staff will issue questionnaires to participants according to a participant schedule created in the trial database through registration of randomisation and 4-week follow-up dates. The information accompanying the questionnaire will remind participants to make use of their Patient Diaries when completing the questionnaires and request that they are returned within 7 days. The time window for a valid response will be defined as 28 days from the issue of the first week 10 questionnaire. If patients have a preference to receive the questionnaire by post, a self-addressed FREEPOST envelope will be included to facilitate postal return. Participants who have opted to complete questionnaires online will be emailed to access the questionnaire. PenCTU staff will monitor the sending and receipt of questionnaires and will issue another questionnaire with a reminder if the first one has not been returned within 10 days from issue. If a completed questionnaire has not been received by 14 days from issue of the first questionnaire, attempts will be made to contact the participant by telephone. Questionnaires may be completed over the telephone if online/postal questionnaires have not been returned or are lost - if participants feel unable to complete the full questionnaire, participants will have the option of completing a subset of the questionnaire booklet by telephone. Priority will be given to collecting the Olerud & Molander ankle score and EQ-5D-5L.

9.6.2. 10-week follow-up CRF completion

Secondary care healthcare resource use information within the 10 week trial period will be collected and transcribed from the hospital records into the CRF by the local research team. Data extracted will include hospital admissions, outpatient visits, including physiotherapy sessions, day case procedures, visits to Accidents & Emergency departments and diagnostic tests or investigations conducted outside the outpatient visit tariff (See Section 7.4 Resource Use).

A small proportion of patients with complicated recoveries may need further clinical evaluation at 12-weeks post-surgery, as per standard care. The research team will

record the date when the patient was discharged or whether they returned to clinic for further follow up at 10 weeks post baseline (12 weeks-post surgery).

Completed CRF pages will be sent to PenCTU using FREEPOST envelopes.

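### The adverse-event objective promises more than is collected, and after week 4 the named SAE routes are thin and not linked to the notes review

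*Protocol*

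**What the plan says.** **Objective.** Protocol 4.2.2 includes: "To determine whether there is a difference in healing, complications and adverse events between the two treatments".

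**What is collected.** Section 11.2 states "Events which are not serious will not be collected or reported as adverse events", with the qualification that "complications listed in section 10.3 will be reported as outcome measures". All SAEs are reportable whatever their cause.

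**When.** Section 7.5: "Serious adverse events will be collected from the point of randomisation at each data collection time point for the duration of the study".

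**How.** Section 11.3 begins "Procedures for collecting and reporting SAEs will be described in a separate trial-specific Work Instruction" and goes on: "SAEs may be identified via patient report at clinic visits or from receipt of resource use questionnaires which indicate a hospital admission".

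**Contacts after week 4.** Table 1 has weeks 5 and 10 completed at home. Section 9.5 says "The 5-week follow-up requires participants to complete a questionnaire comprising the following" and then lists two instruments, the ankle score and EQ-5D-5L. The week-10 booklet (9.6.1) adds resource use and return to activities. For those who do not feel able to finish it, "participants will have the option of completing a subset of the questionnaire booklet by telephone", and the ankle score and EQ-5D-5L come first.

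**Notes review.** Under 9.6.2 the site team extracts admissions and emergency attendances from hospital records for the 10-week period. Section 7.4(ii) limits this to the hospital that performed the surgery and places it at the end of participation.

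**The concern.** Three statements do not fit together. The objective refers to adverse events in general, while the collection rule excludes non-serious events outside a fixed list. Section 7.5 commits to SAE capture at every contact, and week 5 has no means of doing it. The routes named in 11.3 become sparse just when participants leave scheduled clinic follow-up.

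Two things are at stake. A report that follows the objective as written could claim a comparison the data do not contain. SAE ascertainment in the later weeks would also depend partly on who completes a particular questionnaire section. Participants know their allocation (5.2), so completion, and with it ascertainment, could differ by arm. Timeliness matters too: there is no data monitoring committee (13.4), the steering committee takes on safety review (13.5), and related unexpected SAEs go to the ethics committee within 7 or 15 days (11.4.1).

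**Working it through.** The protocol states no figure to reproduce, so the check sets its sections side by side, with two small sums.

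**1. Objective against collection.** Section 11.1 defines an adverse event as any untoward medical occurrence. Section 11.2 keeps two subsets: SAEs, and the complications in 10.3 (blisters, pressure sores, failure of fixation, further surgery, wound infection or breakdown, compartment syndrome, DVT, nerve injury, pulmonary embolism). Complications are already a separate item in the objective, so they do not supply its adverse-event item. What can be compared is listed complications and SAEs.

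**2. Routes by contact after randomisation.**

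| Contact | Clinic report (named in 11.3) | Resource-use form (named in 11.3) | Notes review (9.6.2, not named in 11.3) |
|---|---|---|---|
| Week 4, clinic | yes | yes, completed in clinic | no |
| Week 5, home | no | no | no |
| Week 10, home | none scheduled; some complicated recoveries return | yes, but may be left out by telephone | yes, treating hospital, whole period |

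Neither named route operates at week 5, so 7.5 is not met there.

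**3. Share of follow-up after the last scheduled visit.** Follow-up is 10 weeks from randomisation (5.3) and the clinic visit is at week 4: (10 − 4) / 10 = 60%.

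**4. Longest delay by the questionnaire route.** The week-10 form comes about 6 weeks after the week-4 visit and is valid for 28 days from issue (9.6.1). For an event just after the week-4 visit, the ceiling is 42 + 28 = 70 days, or 10 weeks. Telephone contact starts 14 days after issue, so first attempts fall at about 42 + 14 = 56 days. These are delays to awareness, not expected values.

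**5. What the notes review leaves open.** It does not need a returned form, so treating-hospital admissions are found for everyone. It does not cover other hospitals, which 7.4(iii) leaves to patient report. It also does not reliably reach SAEs without admission, although 11.1 counts death, life-threatening events and persistent disability as serious in their own right. The questionnaire route in 11.3 is likewise worded in terms of admission. The items listed in 9.6.2 are resource-use items, and nothing there tells staff to raise an SAE report.

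**The case against.** The best defence is that detection does not hang on one form. The notes review covers treating-hospital admissions for the whole period. Complications to 12 weeks post-surgery come from patient report, clinical assessment and hospital records (7.2.4). Participants keep a diary as a memory aid (9.3.6), and some complicated recoveries return to clinic. The routes in 11.3 are phrased permissively, and a separate Work Instruction may add others. The between-arm analysis in 12.2.3 names complications, not SAE counts, so the main planned safety comparison has record-based ascertainment.

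Most of this stands. A reader might infer that SAE detection after week 4 rests wholly on a questionnaire; the notes review shows that it does not. A reader might also set a delay of up to 10 weeks against the 24-hour reporting rule, but that clock starts when staff become aware, so late awareness does not breach it. Nor can the 20% over-recruitment in 12.1 be taken as the share of late SAEs missed: it allows for missing data in the main analysis, not for an incomplete week-10 resource-use section.

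The defence does not mend the protocol's own text. A Work Instruction cannot change an objective or make 7.5 agree with 9.5. The diary is not described as a document that is returned. The notes review comes at the end of participation and has no stated link to SAE reporting.

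**Conclusion.** The point holds in a limited form.

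- A general comparison of adverse events cannot be made from the data collected; one of listed complications and SAEs can.
- Section 7.5 is contradicted at week 5.
- For 60% of follow-up, the only scheduled SAE route named in 11.3 is a form that telephone responders may omit.

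The remaining gap is admissions to other hospitals and SAEs without admission among participants who do not complete the resource-use section, together with late detection. Its size cannot be derived, because the protocol gives neither an SAE rate, nor a completion rate for that section, nor the share of admissions elsewhere. Differential ascertainment by arm is possible, not shown.

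This rests on the questionnaires containing what 9.5 and 9.6.1 list. If the unseen Work Instruction already makes the notes review an SAE trigger, the third point shrinks further; the first two are unaffected. The primary outcome, its analysis and the sample size are not touched.

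**What to change.** 1. In 4.2.2, restate the objective as *healing, listed complications and serious adverse events*.
2. In 11.3, name the 9.6.2 notes review as an SAE source for every participant, whether or not a questionnaire comes back.
3. In 9.6.1, add one short question on hospital admission or other serious event to the set given priority by telephone. Covering serious events as well as admissions reaches SAEs without a hospital stay.
4. Reconcile 7.5 with the schedule, either by asking the same question at week 5 or by naming weeks 4 and 10 as the collection points. The first keeps the present commitment and shortens the delay; the second only makes the text accurate.

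The cost is protocol wording and a few seconds per call or form; the notes review is already planned. Limits remain: item 2 does not reach other hospitals, and item 3 helps only those reached by telephone, so participants who return nothing and cannot be contacted are still covered by treating-hospital records alone.
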